4.10.2.3 Multiple Imputation

The MI method specified in this section will either be a sensitivity analysis based on the primary estimand strategy or will be the primary efficacy analysis if no covariance structures for the MMRM converge. The MI will be performed on the FAS. It will involve the following steps:

Step 1 – Imputation Preparation

The dataset of participants with observed values, excluding any values after the ICEs specified in Section 4.10.2, and those needing estimation by multiple imputation will be created. The UACR values will be log-transformed.

Step 2 – Imputation

Imputation is the generation of multiple copies of the original dataset by replacing missing values by using an appropriate stochastic model. The missing data will be imputed using the Fully Conditional Specification (FCS) method. The FCS method is based on an iterative algorithm; at each iteration and for each variable of the prediction model, there is a prediction step and an imputation step. The models used for prediction and imputation will be linear regression models. A total of 200 imputations will be performed using a seed of 12345.

The imputation model will include treatment arms, CSP version (Amendment 2, pre-Amendment 2), diabetes (DKD, non-DM CKD), baseline eGFR strata (≤ 45 versus > 45 mL/min/1.73 m²), baseline log(UACR), and the log(UACR) at each previous post-baseline visit.

Step 3 – Analysis

The analysis step is performed for each of the imputed datasets. The statistical method for analysis of the change in log-transformed UACR from baseline to Week 12 will be ANCOVA and will include the same covariates as the MMRM that is specified in Section 4.10.2.2, except that the visit and by-visit interaction variables – for treatment and baseline log(UACR) – will not be included.

Step 4 – Pooling

Pooling is the combination of the different parameter estimates across the multiple imputed datasets based on Rubin's rules (Rubin, 2004 2004) to produce a unique point estimate and standard error taking into account the uncertainty of the imputation process.

4.10.2.4 Tipping Point Analysis

In order to check the assumption that the missing data is not MAR, a tipping point analysis will be conducted based on the multiple imputation analysis in Section 4.10.2.3. The objective of the tipping point analyses is to identify assumptions about the missing data under which the conclusions from the main analysis change. These tipping point analyses will only be performed if the multiple imputation analysis results show a reduction in UACR for zibotentan 1.5 mg and dapagliflozin 10 mg in combination versus dapagliflozin 10 mg monotherapy.

If there is a reduction in UACR for zibotentan 1.5 mg and dapagliflozin 10 mg in combination versus dapagliflozin 10 mg monotherapy, additional tipping point analyses will be repeated after increasing the imputed log(UACR) values in the zibotentan 1.5 mg and dapagliflozin 10 mg in combination arm by ascending log(UACR) (1, 2, 3... etc.), with the goal to find the "tipping point" that will significantly reverse the analysis result. The smallest delta, for which a reduction in UACR cannot be shown anymore, will be the "tipping point". The delta will only be applied to the Week 12 imputed values for all missing data regardless of the reason for imputation.

For each value of delta, summary tables will include number of participants, the estimates described in Section 4.10.2.2 (such as geometric mean and geometric mean ratio) and their 90% CIs, and corresponding p-values.

This sensitivity analysis will be performed on the FAS.

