4.3 Justification for Dose

Zibotentan

Zibotentan doses of 0.25, 1.5, and 5 mg (hereafter referred to as low, intermediate, and high dose, respectively) were initially selected to characterise the dose-UACR response relationship for zibotentan. Predictions were made using an exposure-UACR response model of clinical data from other ETA receptor antagonists, taking into account differences in PK and potency between the different compounds. Based on this model, 5 mg zibotentan was predicted to achieve a maximal UACR response. In participants with severe renal impairment, a dose of 5 mg will result in plasma exposure similar to that of 10 mg in subjects with normal renal function. Since 10 mg was associated with an increased fluid retention risk in earlier clinical studies, 5 mg was initially selected to be the highest dose used in this study involving a participant population with renal impairment. Based on the rate of fluid retention observed in an ad hoc safety interim analysis, randomisation to 5 mg zibotentan (both monotherapy and in combination with dapagliflozin) has been discontinued. The zibotentan 1.5 mg dose is predicted to cause less fluid retention than 5 mg, while at the same time producing meaningful UACR response, according to the model predictions. The zibotentan 0.25 mg dose was selected to be a minimally clinically relevant dose because it is predicted to produce a 20% or less reduction in UACR in addition to that with dapagliflozin.

Dapagliflozin

Dapagliflozin 10 mg is the approved dose for T2DM, CKD, and HF. 10 mg is the dose tested in DAPA-CKD for patients with CKD and an eGFR > 25 mL/min/1.73m² (NCT03036150).

Based on available preclinical and clinical data, the risk for metabolic drug-drug interactions between zibotentan and dapagliflozin is regarded as low.

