4.10.2.5 Jump to Reference Analysis

The jump to reference analysis assumes that the participants who experience ICEs in the active zibotentan treatment arms immediately change to the mean of the dapagliflozin 10 mg arm at the relevant time point, where the participant's residual relative to that of their treatment arm prior to the ICE is taken into account.

A sequential modelling approach will be used to implement the jump to reference analysis. Firstly, all missing values will be imputed under the MAR assumption as described in Section 4.10.2.3 (Steps I and II). Then data after an ICE in the active zibotentan treatment arms will be reset to missing. Missing data in the active zibotentan treatment arms will be imputed sequentially by visit using observed and imputed data from the reference arm. One imputation will be performed for each imputation already performed under the MAR assumption, thereby maintaining the overall number of imputations at 200, using a seed of 12345. The analysis and pooling steps will then be performed as described in Section 4.10.2.3.

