4.10.2.7 Analysis of Secondary UACR Objectives

Comparison of zibotentan 0.25 mg and dapagliflozin 10 mg combined to dapagliflozin monotherapy (Secondary Objective Related to Primary Objective)

The geometric mean ratio of UACR for the zibotentan 0.25 mg combined with 10 mg dapagliflozin versus 10 mg dapagliflozin alone from baseline to Week 12 will be assessed. The MMRM model as described in Section 4.10.2.2 will be used to extract the results.

The results of the model parameters (estimates, p-values and 90% CIs) will be presented. Analyses and definitions described in Section 4.10.2.1, 4.10.2.2, 4.10.2.3, 4.10.2.4, 4.10.2.5 and 4.10.2.6 will be followed with the treatment arm adjusted as appropriate.

Dose-response Relationship Secondary Objective

The dose-response relationship between different doses of zibotentan/a fixed dose of dapagliflozin and UACR reduction will be characterised by assessing the UACR reduction analysed in the primary objective and the secondary objective related to the primary objective.

In order to select the dose for future studies, a more comprehensive PK analysis, including additional dose and exposure response models and modelling of safety events, will be performed by the AstraZeneca PK team based on subject level data. This will only be done where there is sufficient data that allows the AstraZeneca PK team to perform the modelling.

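### SAP 4.10.2.4 steps the tipping point in whole log units and words its criterion two ways, so the reported value depends on the reading and is coarse for modest effects

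*SAP*

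**What the plan says.** SAP 4.10.2.4 sets the aim of the analysis: to "identify assumptions about the missing data under which the conclusions from the main analysis change". It runs only if the multiple imputation analysis shows a reduction. Imputed Week 12 values in the combination arm, missing for any reason, are then raised "by ascending log(UACR) (1, 2, 3... etc". No value between 0 and 1 is named, and no base is given for the log.

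The criterion appears twice. The goal is a delta "that will significantly reverse the analysis result". The definition is "The smallest delta, for which a reduction in UACR cannot be shown anymore". The section does not say whether a reduction is shown by the point estimate or by a test. The output covers both: "For each value of delta, summary tables will include number of participants", the estimates, their 90% confidence intervals and p-values.

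SAP 4.10.1.1 sets a one-sided test at 0.05. SAP 4.10.2.7 extends the UACR analyses to 0.25 mg, where they "will be followed with the treatment arm adjusted as appropriate". Protocol 4.3 says this dose is "predicted to produce a 20% or less reduction in UACR in addition to that with dapagliflozin".

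**The concern.** A tipping point is useful as a number: how much worse the unobserved values must be before the conclusion changes. Two features of the plan weaken that number.

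First, the two wordings can be read in three ways: loss of significance, the point estimate reaching the null, or significance in the opposite direction. One dataset can give a different answer under each, and the choice could be made after the results are seen.

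Second, the first non-zero step is already large. If a result tips anywhere between 0 and 1, the report shows 1. A fragile result and a fairly robust one then carry the same label.

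**Working it through.** **Inputs.** The documents give 83 (0.25 mg), 166 (1.5 mg) and 166 (dapagliflozin) randomised, a one-sided 5% level with 90% intervals, and a natural-log SD (SAP 3.1, 4.10.1.1, 4.10.2.2, 4.14). The tipping point section has no figure of its own to reproduce. The sample sizes do reproduce: 150/0.9 = 166.7 and 75/0.9 = 83.3, against 166 and 83 in SAP 4.14. That 10% allowance inflates from evaluable participants, who need only one post-treatment UACR. It is not the share imputed at Week 12.

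**Assumptions.** The SD is 0.85 (0.7 to 1.0 checked). The imputed share m is 10% (5% to 25% checked) and is the same in both arms. The observed reduction r is 20%, the top of the Protocol's prediction for 0.25 mg.

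**Step sizes.** exp(1) = 2.72, exp(2) = 7.39, exp(3) = 20.1.

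**Formula.** On the log scale the upper 90% limit at shift d is

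U(d) = ln(1 − r) + m·d + 1.645·SE(d), with

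SE(d)² = SD²·[1/(n1·k) + 1/(n0·k)] + [n1·m(1 − m)·d²/(n1 + n0)]·(1/n1 + 1/n0).

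Here k = 1 − m allows for lost information and k = 1 does not.

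**0.25 mg, 83 versus 166, r = 20%, SD 0.85, m = 10%.**

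- ln(0.80) = −0.2231.
- SE(0) = 0.85·√(1/83 + 1/166) = 0.1143 for k = 1, or 0.1143/√0.9 = 0.1204 for k = 0.9.
- *Loss of significance.* For k = 0.9, U(0) = −0.2231 + 1.645·0.1204 = −0.025, and U(d) = 0 at d = 0.25 (1.28-fold). For k = 1 and the SE held fixed, (0.2231 − 0.1880)/0.10 = 0.35 (1.42-fold). Reported: 1.
- *Point estimate at the null.* 0.2231/0.10 = 2.23. Reported: 3.
- *Literal significant reversal.* With the SE held fixed, (0.2231 + 0.1880)/0.10 = 4.1. Letting the SE grow with d gives values up to 6.4. Reported: 5 to 7.

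A simplified multiple imputation check (no covariates, 200 imputations, Rubin's rules) agrees. The upper limit is −0.024 at delta 0, 0.000 at 0.25 and +0.076 at 1. The point estimate is −0.030 at 2 and +0.066 at 3. The lower limit is −0.016 at 5 and +0.053 at 6.

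**Which observed effects are reported as 1 under the significance reading (SD 0.85, m = 10%, k = 0.9).** The lower edge is 1 − exp(−1.645·SE(0)) and the upper edge is 1 − exp(−0.10 − 1.645·SE(1)). This gives 18.0% to 26.1% for 0.25 mg and 14.9% to 23.4% for 1.5 mg.

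**Range for an observed 20% reduction, significance reading, k = 1 − m.** Entries are exact tipping deltas.

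| Arm, SD | 5% imputed | 10% | 20% |
|---|---|---|---|
| 0.25 mg, 0.7 | 1.22 | 0.58 | 0.25 |
| 0.25 mg, 0.85 | 0.59 | 0.25 | 0.06 |
| 0.25 mg, 0.9 | 0.37 | 0.13 | about 0 |
| 1.5 mg, 0.7 | 1.70 | 0.86 | 0.40 |
| 1.5 mg, 0.85 | 1.24 | 0.60 | 0.26 |

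Entries below 1 are reported as 1 and the others as 2. At SD 1.0 and 10% imputed, a 20% reduction at 0.25 mg is not significant even at delta 0. A 30% reduction at SD 0.85 and 10% imputed tips at 1.50 (0.25 mg) or 1.81 (1.5 mg), both reported as 2.

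**Point-estimate reading, 20% reduction, 0.2231/m.** The deltas are 4.46, 2.23, 1.49, 1.12 and 0.89 at 5, 10, 15, 20 and 25% imputed, reported as 5, 3, 2, 2 and 1. The value falls below 1 once m exceeds about 22%.

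**Interpolation.** In the main case U(0) = −0.025 and U(1) = +0.079, so linear interpolation gives 0.025/(0.025 + 0.079) = 0.24, against 0.25 exactly.

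**The case against.** The strongest reply is that the SAP does contain a definition. The sentence on the smallest delta is explicit, the aim refers to the main conclusions, the main test is fixed elsewhere, and intervals and p-values are tabulated for each delta. On that view the significance reading is the natural one. This stands in part. A reader might infer that the criterion is undefined, and the text does not support that. The gap is narrower: the deciding statistic is not named, and the other wording, about significant reversal, points to a much larger delta.

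A second reply is that no evidence is lost, because the limits at delta 0 and 1 allow interpolation. That is correct, but the SAP does not plan it, and by its own definition the reported value would be the bare whole number. A result that survives delta 1 also survives every smaller delta, so the coarse grid does no harm there.

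A third reply is that the jump to reference analysis already covers departures from missing at random. It does so only for part of the missing data: "Then data after an ICE in the active zibotentan treatment arms will be reset to missing". For Week 12 samples missed without an intercurrent event, the delta shift is the departure that applies.

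Finally, the illustration rests on an assumed SD and imputed share. That is so, and the result of 3 under the point-estimate reading holds only for about 7.5% to 11% imputed.

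**Conclusion.** The point holds as a minor one about a conditional sensitivity analysis. The primary MMRM result is unaffected. With SD 0.85 and 10% imputed, both assumptions, the same 20% reduction at 0.25 mg is reported as 1, 3, or 5 and above, depending on the reading. Under the significance reading, a reported 1 stands for any shift above 1.00-fold and up to 2.72-fold, so it does not grade robustness for modest effects.

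Two stronger inferences should be resisted. One is that the readings always disagree: above about 22% imputed, the point-estimate reading of a 20% effect also gives 1. The other is that the grid is uninformative in general. For larger effects, or about 5% imputed with the lower SDs, the significance reading gives 2 or more and only rounding is at issue. Below about 18% at 0.25 mg in the illustrated case, the result is not significant at delta 0, so it has no significance-based tipping point at all. Because the Protocol predicts at most 20% for this dose, much of its predicted range lies there.

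**What to change.** In SAP 4.10.2.4:

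- Define the tipping point as the smallest delta at which the upper 90% confidence limit of the geometric mean ratio reaches 1. This is loss of significance in the one-sided 5% test of SAP 4.10.1.1. Delete the wording about significantly reversing the result.
- State that the log is natural.
- Use a finer prespecified grid, for example steps of 0.1 log units from 0. Alternatively, keep the whole-unit grid and report the tipping delta interpolated from the upper 90% limits.
- Report the tipping point as a fold change in UACR, with the share of imputed Week 12 values in each arm.

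SAP 4.10.2.7 carries the change to 0.25 mg without further text. The cost is one or two sentences and a longer loop over datasets that are already imputed. The interpolation option needs no extra runs.

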4.10.2.5 Jump to Reference Analysis

The jump to reference analysis assumes that the participants who experience ICEs in the active zibotentan treatment arms immediately change to the mean of the dapagliflozin 10 mg arm at the relevant time point, where the participant's residual relative to that of their treatment arm prior to the ICE is taken into account.

A sequential modelling approach will be used to implement the jump to reference analysis. Firstly, all missing values will be imputed under the MAR assumption as described in Section 4.10.2.3 (Steps I and II). Then data after an ICE in the active zibotentan treatment arms will be reset to missing. Missing data in the active zibotentan treatment arms will be imputed sequentially by visit using observed and imputed data from the reference arm. One imputation will be performed for each imputation already performed under the MAR assumption, thereby maintaining the overall number of imputations at 200, using a seed of 12345. The analysis and pooling steps will then be performed as described in Section 4.10.2.3.

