4.10.2 Analyses of UACR Objectives

4.10.2.1 Primary Estimand for Primary Objective

The primary estimand is a hypothetical estimand such that the treatment effect is quantified in the optimal situation where any potential confounder is minimised. The analysis will be performed on the FAS. The endpoint being assessed is the change in log-transformed UACR from baseline to Week 12. Participants will be included in the analysis if they have a non-missing baseline and at least one non-missing post-treatment visit UACR measurement.

For the intercurrent events (ICEs), if a participant dies, prematurely discontinues study treatment, or uses prohibited medication, the UACR data are treated as missing after the event and no imputation will be performed. The summary measure being evaluated is the geometric mean reduction of UACR from baseline to Week 12.

The estimand is specified through the following definitions of population, variable, treatment condition, ICEs, and population-level summary:

Target population:	Defined by the inclusion/exclusion criteria.
Variable:	Change in log-transformed UACR from baseline to Week 12.
Treatment condition:	Zibotentan 1.5 mg combined with dapagliflozin 10 mg versus dapagliflozin 10 mg.
Intercurrent events:	Death, premature discontinuation from study treatment, or use of prohibited medication (Handled by hypothetical strategy i.e. UACR data are treated as missing after the event. Deaths are expected to be relatively few and will be handled in the context of missing data).
Population-level summary:	Difference in least squares mean change in log-transformed UACR from baseline to Week 12 between zibotentan 1.5 mg combined with dapagliflozin 10 mg and dapagliflozin 10 mg.

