4.11.1 Extent of Exposure

The extent of exposure (days) will be derived for zibotentan and dapagliflozin, combined, as follows:

$$\text{Duration of exposure (days)} = \text{Date of last dose} - \text{Date of first dose} + 1$$

The following extent of exposure summaries will be provided for zibotentan and dapagliflozin (combined):

- Duration of exposure (days)

- A summary of the duration of exposure to treatment (days) and cumulative exposure over time (≥ 1 day, ≥ 8 days, ≥ 22 days, ≥ 43 days, ≥ 64 days, ≥ 85 days), by treatment arm.
- Time on study (days) defined as:
 $Time\ on\ study\ (days) = (Date\ of\ last\ study\ assessment\ or\ Date\ of\ withdrawal) - Date\ of\ randomisation + 1.$

A listing for study drug administration according to protocol and the reason if the study drug administration is not according to protocol will be produced for the Safety Analysis Set.

A Kaplan-Meier figure for time to premature study drug discontinuation will be produced for the Safety Analysis Set. Time to premature study drug discontinuation (days) will be defined as:

- $Date\ of\ premature\ discontinuation\ from\ study\ drug - Date\ of\ first\ dose + 1$ for participants who prematurely discontinue study drug
- $Date\ of\ last\ visit\ day\ in\ the\ treatment\ period - Date\ of\ first\ dose + 1$ for participants who do not prematurely discontinue study drug but are lost to follow-up during the treatment period
- $Minimum(Withdrawal\ of\ consent\ date, Date\ of\ death, Date\ of\ Visit\ 7, Date\ of\ study\ day\ 86) - Date\ of\ first\ dose + 1$ for any other participants who do not prematurely discontinue study drug.

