4.15 Changes in the Conduct of the Study or Planned Analysis

Echocardiography is included as an exploratory variable for efficacy assessments in the CSP but is included as a safety variable related to the safety objective in this SAP.

The CSP states that for the primary endpoint, no imputation is performed for UACR data that is treated as missing after the ICEs. If there are convergence issues with the MMRM proposed for the primary analysis, an ANCOVA with MI will be performed, meaning there is the possibility of imputation being performed. Regardless of the approach that will be taken for the primary analysis, sensitivity analyses will be performed that includes imputation for UACR data that is treated as missing after the ICEs.

The CSP states that the secondary variables of BP and eGFR will be analysed using ANCOVA but they will be analysed using a MMRM for consistency with the primary efficacy variable analysis, with an option for ANCOVA if none of the covariance structures converge.

The CSP does not include the phrase “or at a time selected by the sponsor” in relation to the first interim analysis for the planned timings of the interim analysis.

The CSP states that lost to follow-up is an ICE but it is not defined as an ICE in this SAP. It will be handled in the framework of missing data.

The CSP states that ABPM includes all participants in the FAS who have valid ambulatory BP data for change from baseline analysis, but as per SAP this analysis set will include all participants in the Descriptive Analysis Set who have valid ambulatory BP data for change from baseline analyses.

The CSP states that changes from baseline of ECG parameters will be listed, but as per SAP only the abnormalities (values outside the reference ranges) will be presented in the listings.

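### Jump-to-reference in SAP 4.10.2.5 applies only after an intercurrent event, so zibotentan participants lost or withdrawn without a recorded discontinuation stay under MAR and the check is slightly lenient

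*SAP*

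**What the plan says.** **Who jumps.** SAP 4.10.2.5 opens: "The jump to reference analysis assumes that the participants who experience ICEs in the active zibotentan treatment arms immediately change to the mean". The mean in question is that of the monotherapy comparator.

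**How it is done.** There are three steps. Every missing value is filled under MAR by the multiple imputation of SAP 4.10.2.3. Next, "Then data after an ICE in the active zibotentan treatment arms will be reset to missing". Finally, "Missing data in the active zibotentan treatment arms will be imputed sequentially by visit using observed and imputed data from the reference arm".

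**What counts as an ICE.** SAP 4.10.2.1 lists: "Death, premature discontinuation from study treatment, or use of prohibited medication". SAP 4.15 records the departure from the protocol: "The CSP states that lost to follow-up is an ICE but it is not defined as an ICE in this SAP". It assigns such cases to the missing-data framework instead. Protocol 9.4.2.1 does list loss to follow-up as an ICE.

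**Status of a lost participant.** Protocol 7.3 regards a participant who cannot be reached as withdrawn from the study. Protocol 7.2 says that withdrawal also ends study intervention. SAP 4.11.1, in its rule for time to drug discontinuation, has a separate class for participants "who do not prematurely discontinue study drug but are lost to follow-up during the treatment period".

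**The other stress test.** The tipping-point analysis (SAP 4.10.2.4) applies its delta to the Week 12 "imputed values for all missing data regardless of the reason for imputation".

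**The concern.** Jump-to-reference is in the plan to show whether the result survives if zibotentan participants with missing data lose the add-on effect. Once the MAR step has run, nothing is missing except what is then reset, and the reset covers post-ICE data only. A participant who is lost without a recorded ICE is never drawn from the dapagliflozin arm. The value that stays in place comes from a model that conditions on the participant's own arm and excludes post-ICE values, so it carries the zibotentan effect.

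These are people whom the protocol regards as off study drug. One class of drop-out therefore remains under the very assumption that the analysis is meant to test. The SAP discloses that loss to follow-up is no longer an ICE, but it does not say that this narrows jump-to-reference. At stake is how far this one sensitivity analysis can be trusted. The primary result does not depend on it.

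**Working it through.** **1. Inputs in the documents.** SAP 4.14 gives 150 evaluable participants in each main arm and 75 in the 0.25 mg arm, with 10% drop-outs. The inflation reproduces to rounding: 150/0.9 = 166.7 against 166 stated, 75/0.9 = 83.3 against 83 stated, and 166 + 166 + 83 = 415. An evaluable participant needs only one post-treatment UACR, so the 10% is not a rate of loss to follow-up by Week 12. No such rate is given. The assumed effect and SD are redacted.

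**2. Assumptions.** True geometric mean ratio (GMR) 0.60 to 0.80, share lost or withdrawn without an ICE (p_L) 1% to 10%, share with an ICE (p_ICE) 0% to 5%, SD 0.85 on the log scale.

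**3. Formula.** With δ = ln(GMR), the expected Week 12 log effect is

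- rule as written: (1 − p_ICE) × δ
- lost and withdrawn participants also jump: (1 − p_ICE − p_L) × δ

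The difference is p_L × |δ|. Relative to the estimate as written it is p_L/(1 − p_ICE).

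**4. Results.** For GMR 0.70, |δ| = 0.357, and p_L of 2%, 5% and 10% gives shifts of 0.0071, 0.0178 and 0.0357.

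| True GMR | p_ICE | As written | p_L = 2% | p_L = 5% | p_L = 10% |
|---|---|---|---|---|---|
| 0.60 | 0% | 0.600 | 0.606 | 0.616 | 0.631 |
| 0.70 | 0% | 0.700 | 0.705 | 0.713 | 0.725 |
| 0.80 | 0% | 0.800 | 0.804 | 0.809 | 0.818 |
| 0.70 | 5% | 0.713 | 0.718 | 0.725 | 0.738 |

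Of 166 participants, 2% to 5% is about 3 to 8 people. In the rows with no ICEs, jump-to-reference as written equals the MAR analysis.

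**5. Check by simulation.** A simplified version of the imputation rule was run (166 per arm, 4,000 runs, SD 0.8, correlation 0.6, true reduction 30%). With 5% ICE and 5% lost, the reduction was 28.8% as written and 27.5% if all jump. With 0% ICE and 10% lost, it was 30.1% and 27.5%. The formula gives 28.7% and 27.5%, and 30.0% and 27.5%.

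**6. Size against the standard error.** For the 1.5 mg comparison, SE = 0.85 × √(2/150) = 0.098. A shift of 0.0071 to 0.0178 is 0.07 to 0.18 SE, and the 10% bound is 0.36 SE. Even at that bound, the ratio of effect to SE falls only from 0.357/0.098 = 3.6 to 0.321/0.098 = 3.3, against a one-sided critical value of 1.645. For 0.25 mg at GMR 0.80, SE = 0.85 × √(1/75 + 1/150) = 0.120, and p_L of 2% to 10% shifts the estimate by 0.04 to 0.19 SE.

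**The case against.** **Lost participants may already count as discontinued.** Premature discontinuation of treatment is an ICE. Protocol 7.2 and 7.3 together would support coding a lost participant that way, and such a participant would then jump. The class in SAP 4.11.1 comes from a Kaplan-Meier convention, which also places deaths among those who did not stop drug early although death is an ICE. So it does not map ICE status. This stands as a limit: a reader might infer that every lost participant escapes the jump, and the documents do not show that. They leave it to how each case is recorded, and SAP 4.15 points away from treating loss as an ICE.

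**The choice is disclosed and coherent.** Reference-based imputation after ICEs with MAR elsewhere is a legitimate pairing, and the algorithm matches its opening sentence. That is fair. What is missing is a reason for keeping under MAR those whom the protocol regards as off drug.

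**The tipping point covers them.** It does, and SAP 4.10.2.7 carries it to 0.25 mg. Its first step of 1 log unit (×2.72) is 1/0.357 = 2.8 times the full loss of a 0.70 effect, so it is the harsher test. A reader might call the two analyses contradictory, but they differ in scope and complement each other. The coarse step does skip the range that jump-to-reference would examine.

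**Some lost participants still hold drug.** Bottles contain 28 units (protocol Table 4). If one bottle of each product is given per dispensing visit (an assumption), supply from Day 64 lasts to Day 91, past the Week 12 visit on Day 84. Supply from Day 43 ends on Day 70. The objection therefore stands for losses after Week 9 but not for earlier ones.

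**Conclusion.** The gap is real on the SAP text but minor. Zibotentan participants who are lost or withdraw without a recorded ICE keep own-arm MAR values in an analysis intended to remove the zibotentan effect from drop-outs. At an assumed GMR of 0.70, with 2% to 5% lost in this way, the estimate would move from 0.700 to about 0.705 to 0.713. The 0.725 at 10% is an extreme bound.

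Three stronger readings go too far:

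- **The error always favours zibotentan.** It does so only if zibotentan lowers UACR. With no effect the shift is zero, and with a harmful effect it reverses.
- **The 10% drop-out allowance is the loss rate.** It inflates evaluable to randomised numbers for all causes.
- **The trial's conclusion is at risk.** The primary estimand, the MMRM and the sample size are untouched, and under the assumptions above the shift is well below half a standard error.

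The figures rest on assumed effect, SD and loss rates. The mechanism rests only on the text.

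**What to change.** Amend SAP 4.10.2.5 in two places.

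- **Reset step.** Keep the reset of all post-ICE data, observed or imputed, and add: *In the active zibotentan arms, monotone missing UACR data after loss to follow-up or withdrawal from the study, counted from the first visit missed after the last UACR collected, are also reset and imputed from the reference arm. Intermittent gaps remain as imputed under MAR.*
- **Opening sentence.** Extend it to name loss to follow-up and study withdrawal beside ICEs, and refer to the residual before whichever event applies.

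With this rule, the result no longer depends on whether a lost participant was also recorded as having discontinued drug. The primary estimand and the MMRM need no change.

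The cost is one extra flag in the imputation program, two amended sentences and a slightly less favourable sensitivity estimate. For a participant lost after Week 9 who still holds drug the assumption is conservative, and the SAP can say so.
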